
Aim 2: Younger Americans with COVID-19 infection have a higher rate of hospitalization and need for mechanical ventilation compared to younger citizens of other countries. One potential explanation is high obesity prevalence. Obstructive sleep apnea is present in over 50% of obese individuals and obesity further compromises lung compliance and ability to handle increased ventilatory demand seen in COVID-19 patients with related lung injury. Further, COVID infected individuals with OSA may be at higher risk for progression from mild pneumonia to ARDS however this remains to be determined. Therefore in Aim 2, we will determine if obstructive sleep apnea (OSA) is associated with increased hospitalizations and mechanical ventilation in COVID-19 suspected or confirmed patients. This will be achieved primarily through our control group (not receiving PAP therapy but will receive home sleep apnea testing). This is of vital importance as the primary treatment of OSA is CPAP and there are more than 8 million CPAP users in the United States. This treatment can therefore be leveraged to treat mild respiratory distress in COVID infected OSA patients in the face of a crisis with hospital and ventilator shortage. We hypothesize that obese patients with COVID-19 infection are more likely to be hospitalized or receive mechanical ventilation compared to non-obese individuals with COVID-19 infection. In exploratory analysis, we will also assess if OSA is an independent risk factor for hospital admission or death in our control group. We expect obesity and OSA to be correlated and will determine the independent impact of each of these on our primary endpoint.

**Aim 3:** To leverage EHR to determine a risk score to predict readmission to the Emergency room in COVID-infected or suspected patients. This aim will be done simultaneously while Aims 1 and 2 are ongoing and will be implemented in real-time to identify high-risk patients.

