- 8) All patients will be contacted every 6-12 hours to complete follow up assessments. These follow ups will be done via a phone call. If the timing of these follow ups fall between 10pm-6am, the follow up will be deferred until after 6am. After 72 hours, all patients will then be contacted daily until day 14 from randomization. After day 14, research staff will continue to monitor the medical charts for any visits to the hospital. One last contact will be made on day 28.
- 9) After 72 hours, patients will be asked to discontinue using the CPAP and pulse oximeter. If patients wish to continue to use the CPAP, they may do so for up to 7 days from time of randomization.
- 10) The research staff will continue to call all patients daily (after the 72 hour mark) to assess symptoms.
- 11) The patients can also choose to monitor their oxygen saturation beyond the 72 hours of treatment.
- 12) CPAP download is available continuously however we will download data on usage, pressure, leak daily and make adjustments to the mask or CPAP pressure as needed for patient comfort. For patients experiencing significant trouble tolerating high pressure, we will decrease CPAP from 8-10 cm to a fixed CPAP of 5 cm for 2-4 hours after which we will raise it back to 8-10cm for the

- duration of the study. If the patient is not able to tolerate the pressure again, we will reduce it back to 5cm of water pressure for several hours before increasing the pressure. This will be continued until the patient withdraws or 72 hours are completed, whichever occurs first.
- 13) Patients will be asked to track their own oxygen saturation using the provided pulse oximeter and report it when we contact them for the 6-12 hour follow up calls/surveys.
- 14) The sleep apnea test will provide continuous oxygen and breathing data for a period of 12 hours during the 72 hours and will also provide information on oxygen saturation while the patient is asleep.

The outline of the forms that correspond to the study visits can be found in the Appendix, Figure 1. All of these forms are subsequently included in the following appendicies.

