Early Continuous Positive Airway Pressure (CPAP) in COVID-19 Confirmed or Suspected Patients

PI: [name], MPH

NCT04390191

Document Date: 4-21-2020

General Design Issues

This is a prospective, single-center, parallel group, open-label, randomized clinical trial. The primary objective is to evaluate the efficacy and safety of the use of CPAP versus control in COVID-19 suspected or confirmed patients with pneumonia or respiratory illness. The primary efficacy endpoint is a **non-weighted composite endpoint comprised of the following components:**

- All-cause mortality within 14 days of randomization
- Hospital Admission (including ED visit) within 14 days of randomization
- Oxygen saturation less than 90 during the 72-hour observation period from randomization
- Absolute reduction in oxygen saturation of more than 4% during the 72-hour observation period from randomization

Sample Size and Power

Sample size was restricted by the availability of CPAP and the need for rapid answers during the exceptional health care challenges and fluid epidemiological conditions. The table below summarizes the effect sizes (% reduction in the proportion of patients with a negative outcome) that can be detected with sufficient power (>80%) under several scenarios assuming a total sample size of 200 patients (100 per arm) using a two-sided Fisher's exact test at the 0.05 significance level. Preliminary data from the Mount Sinai Health System indicated that about 25% of the COVID-19 positive patients with respiratory distress were sent home and subsequently hospitalized. We assumed that the proportion of patients with a negative outcome in the control group will range between 25% to 50%. Depending on these values, the planned sample size will allow us to detect a relative treatment reduction between 64% to 42% in this range (see table below).

Furthermore, given the short follow-up time for the assessment of the primary outcome and the nature of the primary outcome, we anticipate that we will be able to assess the primary outcome on all patients. We also believe that patients will be supportive of this intervention and compliant with treatment, so sample size was not adjusted for drop-out rates. However, if due to unforeseen circumstances we will conservatively set any missing primary outcome assessment to "negative" or "failure". Power calculations were performed in SAS 9.4 using the PROC POWER function.

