Proportion of patients with Negative outcome	Control	0.25	0.30	0.35	0.4	0.45	0.5
	СРАР	0.09	0.12	0.16	0.20	0.25	0.29
	Relative reduction in CPAP arm (%)	64	60	54	50	44	42

Randomization Design and Procedure

Patients will be randomized using a 1:1 allocation to CPAP versus control group. The randomization will be stratified by BMI ($\geq=30$ and ≤30), gender and age (≤60 , $\geq=60$). A random permuted block design will be employed, with random blocks of size 2 and 4.

Data Monitoring and Analysis

Primary Efficacy Analysis

The primary efficacy endpoint is the proportion of patients with a negative composite endpoint within 14 days of randomization and will be compared between CPAP and control groups. The null hypothesis is that the proportion of patients with a negative outcome will be the same between patients randomized to CPAP versus control arm. This hypothesis will be tested using a two-sided Fisher's exact test at 0.05 alpha level. The primary analysis will be conducted according to the intention-to-treat principle.

Early stopping rule: If three deaths are observed in the CPAP group, enrollment will be halted pending DSMB review and recommendations. As of April 03, the death rate for COVID-19 positive patients in NYC was 2.99% [95% Clopper Pearson CI= 2.986, 2.997]. The rate is expected to be lower for our patient population. As such, 3 deaths among 100 patients will indicate a proportion of 3% [95% CI: 2.57%, 3.78%].

Analyses of Secondary Endpoints

Safety

Safety analyses will be conducted according to randomization assignment and treatment actually received. Adverse event rates will be calculated as the ratio of the total number of events over 14 days divided by total patient-days at risk for the specific event from randomization. A Poisson model with robust variance estimation will be used to compare SAEs between CPAP and control patients.

Time-to-events outcomes

Time from randomization to event outcomes (Hospitalization or ED visit, ICU admission, intubation and mechanical ventilation) within 14 days of randomization will be compared between randomization groups using a log-rank test or Gray's test in the presence of competing risk of death. In addition, survival at days 14 and 28 post-randomization will be described by Kaplan-Meier curves and a log-rank test will be used to compare survival between the two groups.

Respiratory Function

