- Improvement in oxygen saturation will be compared between randomization groups using linear mixed-effect models with patient as a random effect.
- Improvement in respiratory symptoms, as measured by the Clinical COPD Questionnaire, will be compared between randomization groups using linear mixed-effect models with patient as a random effect.

Conversion rate of family members

The conversion rates (yes/no) of family members in the two randomization groups will be compared using a Fisher's exact test. If there is sufficient variability, a zero-inflated count model may be considered as well.

Continuation of CPAP for greater than 72 hours

The proportion of patients in the CPAP group who elected to continue CPAP use after 72 hours will be estimated along with 95% Coppler-Pearson confidence intervals.

Exploratory Analyses

Exploratory analyses will be conducted similarly as the primary analysis except that it will be only in the control arm comparing OSA versus non-OSA patents and obese vs non-obese patients.

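### The only planned OSA analysis most naturally uses the primary composite, which lacks a ventilation component and includes desaturation in the window where OSA is measured; Aim 2's clinical outcomes need their own analysis

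*SAP*

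**What the plan says.** Protocol section 1.2, Aim 2, states its lead question as "we will determine if obstructive sleep apnea (OSA) is associated with increased hospitalizations and mechanical ventilation in COVID-19 suspected or confirmed patients". It adds, as exploratory, "we will also assess if OSA is an independent risk factor for hospital admission or death in our control group". Its last sentence says of obesity and OSA that the study "will determine the independent impact of each of these on our primary endpoint". So three outcomes are named: hospitalization and ventilation, admission or death, and the primary endpoint.

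The SAP's Exploratory Analyses section has one sentence for all of this: "Exploratory analyses will be conducted similarly as the primary analysis except that it will be only in the control arm", comparing OSA with non-OSA and obese with non-obese patients. The primary analysis it points to compares the proportion with a negative composite: "This hypothesis will be tested using a two-sided Fisher's exact test at 0.05 alpha level".

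The composite (SAP, General Design Issues; protocol section 1.3) has four components: death and hospital admission including ED visit, both within 14 days; saturation below 90 within 72 hours; and "Absolute reduction in oxygen saturation of more than 4% during the 72-hour observation period from randomization". Mechanical ventilation is not a component.

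OSA status comes from the WatchPAT. Protocol section 7.1, item 14, places its 12-hour recording within the 72 hours and says the test "will also provide information on oxygen saturation while the patient is asleep".

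**The concern.** There are two problems.

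First, the questions that Aim 2 puts first have no analysis of their own. The SAP's time-to-event analyses of hospitalization, ICU admission and ventilation compare randomized groups, not OSA groups.

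Second, exposure and outcome may share a measurement window and a physiological mechanism. OSA causes saturation to fall during sleep. If such falls can meet a saturation component, OSA patients reach the composite more often even when OSA has no bearing on admission, ventilation or death.

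What is at stake is interpretation. The protocol ties Aim 2 to the possible use of CPAP in infected patients with OSA. A positive composite result could be taken as evidence that OSA worsens the course of COVID-19 when it shows only that OSA patients desaturate asleep. Adjusting for obesity would not remove this.

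**Working it through.** **Check of the method on the SAP's own figures.** The SAP gives no figure for the OSA analysis, but it does give a power table for 100 per arm with a two-sided Fisher's exact test at 0.05. Full enumeration of the two binomial distributions gives power of 0.830, 0.854, 0.843, 0.845, 0.809 and 0.833 for the six pairs. The relative reductions are 64.0, 60.0, 54.3, 50.0, 44.4 and 42.0%. All powers exceed 80% and the table reproduces.

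**Inputs for the OSA comparison.**
- 100 controls (SAP, Sample Size and Power).
- Admission or death 25% in both OSA and non-OSA controls, that is, no OSA effect. The 25% is the SAP's preliminary hospitalization figure; its use here is an assumption.
- 50 of the 100 controls with OSA. Assumed: the protocol says only that OSA is present in over half of obese individuals.
- Share meeting a saturation component: 10% without OSA, and 20%, 30% or 50% with OSA. Assumed, and independent of clinical events.

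**Formula.** Composite risk = 0.25 + (1 − 0.25) × q, where q is the share meeting a saturation component.
- Non-OSA, q = 0.10: 0.25 + 0.75 × 0.10 = 0.325
- OSA, q = 0.20: 0.25 + 0.75 × 0.20 = 0.400
- OSA, q = 0.30: 0.25 + 0.75 × 0.30 = 0.475
- OSA, q = 0.50: 0.25 + 0.75 × 0.50 = 0.625

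**Probability that the two-sided Fisher test gives p ≤ 0.05, 50 vs 50.**

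| Outcome | OSA | Non-OSA | All controls | P(significant) |
|---|---|---|---|---|
| Admission or death only | 25% | 25% | 25% | 3% |
| Composite, q 10% vs 10% | 32.5% | 32.5% | 32.5% | 3% |
| Composite, q 20% vs 10% | 40.0% | 32.5% | 36.25% | 9% |
| Composite, q 30% vs 10% | 47.5% | 32.5% | 40.0% | 27% |
| Composite, q 50% vs 10% | 62.5% | 32.5% | 47.5% | 83% |

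The 50/50 split is not critical. With 30 OSA patients the last three rows become 9%, 27% and 78%; with 40 they become 9%, 27% and 82%. Admission or death alone stays at 3 to 4%. All the overall composite rates shown lie within the SAP's assumed control range of 25 to 50%.

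**Which readings count.** The endpoint wording names no device, no baseline and no time of day, so it does not exclude sleep. Against that, section 7.1 (items 5, 8 and 13) has patients report oximeter values at follow-up calls, and calls falling between 10pm and 6am are deferred. On that route few sleep readings would enter, and the two q values would lie close together, near the 3% row.

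**Controls with no OSA status.** Equipment arrives between the same day and 48 hours after ordering (section 7.1, item 4). A control who is admitted or dies before the recording would probably have no OSA result. The SAP's rule that a missing primary outcome counts as failure does not address a missing exposure.

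**The case against.** The strongest reply is that the composite is a protocol-named Aim 2 outcome, so analysing OSA against it follows the text. That stands. A reader might infer that the SAP departs from the protocol by using the composite, or tests nothing that Aim 2 names. Neither is supported: Aim 2's last sentence names the primary endpoint, and death and admission are two of its four components. A ventilated patient would also normally be counted through admission. What is missing is an analysis of the clinical outcomes without the saturation components.

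A reader might also infer that the circularity is built into the design. The documents do not go that far. No passage says WatchPAT traces score the endpoint, and the oximeter route is patient report at calls outside the night hours. The table in protocol section 10.2 links the fall of more than 4% to breathing symptoms and requires no reporting of a decrease without them, which also points away from silent night-time dips, although saturation below 90 carries no symptom condition there. The overlap therefore depends on a scoring rule that is not stated.

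Two smaller objections also stand. The SAP sentence could mean only the same method, with the outcome left open; that would be a gap in itself. And obesity is defined by BMI, which shares no measurement with the outcome, so the overlap argument does not carry over directly to it.

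**Conclusion.** The concern holds in limited form. The SAP should not leave the composite as the sole OSA outcome when Aim 2 leads with hospitalization, ventilation and death. That part needs no assumption beyond the natural reading of the SAP sentence.

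The size of the distortion is conditional. If sleep readings count, the chance of a significant OSA result with no OSA effect on admission or death rises from 3% to between 9% and 83% over the range shown, and it depends on assumed desaturation rates that the documents do not give. A 70% vs 10% contrast would exceed 99%, but it implies 55% of controls with a negative outcome ((77.5% + 32.5%) / 2), above the SAP's range, so it is not relied on. If only call-reported readings count, the distortion is much smaller.

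The analysis is exploratory and confined to controls. The randomized CPAP comparison, its sample size and the safety analyses are untouched.

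**What to change.** In the SAP's Exploratory Analyses:
- Make the main OSA outcome hospital admission (including ED visit), mechanical ventilation or death within 14 days, without the two saturation components.
- Report the same clinical outcome for obesity, because Aim 2's hypothesis for obesity concerns hospitalization and ventilation. The reason here is consistency with the aim, not overlap.
- Keep the full composite as a supportive analysis, in line with Aim 2's last sentence, and state which saturation readings count toward it.
- Report how many controls had an event before the WatchPAT recording, and how many never had one. Add a landmark analysis starting after that night as a sensitivity analysis. The landmark sets early events aside by rule and does not recover them, so the counts must accompany it.

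The cost is SAP wording and one outcome variable built from data already collected. The downside is precision: in the illustration, about 25 clinical events among 100 controls against 36 to 48 composite events, hence wider intervals. That is acceptable in an exploratory analysis.

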## **APPENDICES**

## FORMS

## SCREENING FORM

## **Screening Form**

1.	Source of participant's referral? (check one)
	Mount Sinai Main ED
	Mount Sinai ED Surge Space
	ED Precision Recovery Program
	□ EPIC
	□ other means, specify:
Demo	graphics and Subject History Form :
2.	Patient's demographic information was obtained via:  ☐ Chart Abstraction ☐ Oral Interview
3.	participant's current age?
4.	What is the participant's biological sex?  ☐ Male ☐ Female
5.	What is the participant's race (check all that apply)?
	American Indian or Alaska Native
	Asian
	Black or African American
	White or Caucasian
	Native Hawaiian or Other Pacific Islander
	Other (please specify):
	Unknown or Not Reported
6.	What is the participant's ethnicity?
	Hispanic or Latino
	Not Hispanic or Latino
7.	What is participant's BMI?

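### Aim 2 is tested only by separate yes/no contrasts in about 100 controls, which leaves graded BMI and sleep-test data unused and cannot separate the effects of obesity and OSA

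*SAP*

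**What the plan says.** The SAP's Exploratory Analyses section is one sentence. It says the analyses follow the primary analysis, except that "it will be only in the control arm comparing OSA versus non-OSA patents and obese vs non-obese patients". The SAP's Primary Efficacy Analysis compares proportions with the composite endpoint by a two-sided Fisher's exact test at 0.05. Fisher's test is not named again under Exploratory Analyses, so its use there is inferred from that reference.

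The protocol asks for more. Aim 2 (section 1.2, Objectives) states: "We expect obesity and OSA to be correlated and will determine the independent impact of each of these on our primary endpoint".

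Both exposures are measured on a scale. The Screening Form, item 7, asks "What is participant's BMI" as an open field. Section 7.1, item 14, says "The sleep apnea test will provide continuous oxygen and breathing data for a period of 12 hours". Aim 1 defines obesity as BMI of 30 or more. Neither document gives a cut for OSA, names a severity index, or states an effect size or power for Aim 2.

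**The concern.** There are two separate problems.

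- **Independence.** The protocol expects obesity and OSA to be correlated and wants the effect of each apart from the other. Two unadjusted tables show only marginal associations. If just one exposure matters, the other will tend to look associated through the correlation, and nothing in the planned analysis can tell the two situations apart.
- **Information.** A split treats BMI 30 like BMI 45 and does the same for sleep-test severity on either side of whatever OSA cut is used. If risk rises steadily with the exposure, this costs power in a comparison limited to about 100 people. For OSA the result also depends on a cut that has not been fixed, so it could be chosen after the data are seen.

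At stake is how useful Aim 2 will be. The randomized comparison of CPAP with control is not affected.

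**Working it through.** **Inputs from the documents.** 200 patients allocated 1:1, so about 100 controls; control event rate 25% to 50%; two-sided Fisher's exact test at 0.05 (SAP, Sample Size and Power; Primary Efficacy Analysis); obesity at BMI of 30 or more (protocol, Aim 1).

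**Assumptions not in the documents.** Odds ratio (OR) per SD of the exposure 1.5-2.0; 20-70% of controls in the exposed group; a normally distributed exposure; log-linear risk; for the joint model, a correlation of 0.5 between the exposures. The only prevalence given is OSA in over half of obese people. Obese patients are to be oversampled by an unstated amount.

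**Step 1: the plan's own figures.** The SAP's power table concerns CPAP against control. Exact Fisher power at 100 per arm for its six scenarios is 83.0, 85.4, 84.3, 84.5, 80.9 and 83.3%, all above the stated 80%. The relative reductions also agree, for example (0.25 - 0.09)/0.25 = 64%. The table is sound but does not cover Aim 2, which has half the patients and groups of unknown size.

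**Step 2: graded term against split.** Simulate 100 controls with logit(p) = a + b·x, where x is the standardised exposure, b = ln(OR per SD), and a is set to give the overall event rate. Compare three tests at two-sided 0.05: (i) likelihood-ratio (LR) test of x in logistic regression; (ii) Fisher's test on x cut into exposed and unexposed; (iii) LR test on that same split. Then (i) - (ii) is the whole gap, (i) - (iii) the part due to splitting, and (iii) - (ii) the part due to Fisher's conservatism. With 2,500 runs the simulation error of one power is at most 100·√(0.25/2500) = 1.0 point.

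| Events | Exposed | OR per SD | Risk, exposed / unexposed | (i) Graded | (ii) Fisher | (iii) LR on split | Whole gap | Splitting | Fisher |
|---|---|---|---|---|---|---|---|---|---|
| 25% | 50% | 1.5 | 31% / 19% | 40.9 | 23.6 | 27.8 | 17.3 | 13.1 | 4.2 |
| 25% | 50% | 2.0 | 35% / 15% | 80.4 | 55.9 | 62.1 | 24.5 | 18.3 | 6.2 |
| 50% | 50% | 1.5 | 58% / 42% | 49.7 | 32.2 | 35.7 | 17.5 | 14.0 | 3.5 |
| 50% | 50% | 2.0 | 63% / 37% | 90.6 | 72.1 | 75.4 | 18.5 | 15.2 | 3.3 |
| 25% | 60% | 2.0 | 32% / 14% | 81.6 | 52.0 | 59.4 | 29.6 | 22.2 | 7.4 |

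Two further cells show the spread. With 25% events, 40% exposed and OR 1.5, power is 41.5% against 24.5%, a gap of 17.0 points. With 25% events, 70% exposed and OR 2.0, it is 81% against 43%, a gap of 38 points. Over 20-70% exposed and OR 1.5-2.0 the whole gap is about 16-39 points. About 12-30 of that is due to splitting and 2-10 to Fisher's conservatism.

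**Step 3: how far the figure moves.** OR 1.3 gives 8-14 points and OR 2.5 gives 9-31. With 10-15% or 80% exposed, at OR 1.5-2.0, the gap is 21-56. A strongly skewed exposure can take it to nearly 60.

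**Step 4: the reverse case.** Let risk jump only at the cut. With 30% exposed and risks of 40% against 15%, Fisher's test has 73.0% power and the graded term 57.0%, so the split leads by 16.0 points. With 50% exposed and risks of 60% against 35%, it is 68.0% against 53.4%, a lead of 14.6. This set gives leads of 13-19 points. A wider set of steps (OR 2-4) gives roughly 5-22.

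**Step 5: independent effects.** Let only the first exposure affect risk, with a correlation of 0.5 between the two. In separate graded models, the second exposure is significant in about 15-34% of runs although it has no effect of its own. Replacing the splits with two separate graded models is therefore not enough. In a joint model the adjusted graded term has about 7-27 points more power than the unadjusted Fisher split. That is less than in Step 2, because adjustment costs precision and answers a harder question. With 25 to 50 events and two terms there are 25/2 = 12.5 to 50/2 = 25 events per term, so the joint model is feasible.

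**The case against.** The strongest reply is that the obesity contrast is the question asked. Aim 2 words its hypothesis as obese against non-obese patients, and BMI 30 is both the trial's definition of obesity and a randomization stratum. The SAP labels these analyses exploratory, and the protocol uses the same word for the OSA risk-factor analysis in controls. This stands. It is why the yes/no contrast should be kept, and why the point is minor.

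It is also fair that no single power loss belongs to this plan. A reader might infer that the split costs a known number of points. The documents give no slope, no exposed share and no OSA cut, and the sign reverses under a true step. Nor do they say that a non-significant result will be reported as absence of association, or that mild and severe sleep apnea will be pooled, since no cut is stated. A graded sleep index is itself an inference from the continuous recording.

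What the reply does not meet is the promise of independent impact. Exploratory status does not let two unadjusted tables separate correlated exposures.

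**Conclusion.** The point holds as a cheap improvement of low severity. Two parts follow from the text alone: the planned contrasts leave graded BMI and sleep-test data unused, and they cannot deliver the independent effects promised in Aim 2.

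The size is conditional on the assumptions listed under the check. Under them, a single graded term gains about 16-39 points over the Fisher split, and a mutually adjusted term about 7-27 points. The split is better by roughly 5-22 points if risk changes only at the cut. The documents do not support calling the obese against non-obese contrast wrong, since it answers the hypothesis as worded.

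**What to change.** In SAP Exploratory Analyses, make the main Aim 2 analysis one logistic regression of the primary composite in the control arm. Enter continuous BMI and a continuous sleep-apnea severity measure from the home sleep test together. Name the measure and its scale in advance, for example log(index + 1) so that zero values are handled. Report each adjusted OR per SD with its 95% confidence interval.

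Keep two companion analyses: obese against non-obese at BMI of 30 or more, which matches the worded hypothesis, and OSA yes/no at a cut fixed before analysis.

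The cost is a few lines in the SAP, with no new patients, visits or data. The drawback is that the model assumes a roughly log-linear relation and loses power if there is a true threshold, which the retained contrasts cover.
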